3. OBJECTIVES AND ENDPOINTS

OBJECTIVES	ENDPOINTS
Primary	
To compare the safety and accuracy/efficacy of low dose Y90 resin microspheres and MAA in predicting the actual dose delivered to the tumor, liver, and lung after Y90 therapy.	
 • Safety: adverse events related to Y90 radioembolization and angiography will be document by physical examination, clinical laboratory test and cross-sectional imaging. • Accuracy/Efficacy: The accuracy/efficacy of MAA as a predictor of therapeutic Y90 distribution will be compared to that of low-dose Y90.
Secondary	
 1. To Identify tumor dose response thresholds (TDRT) and tumor dose distribution in patients with HCC treated with Y90 resin microspheres. 2. To optimize low dose Y90 techniques in predicting TNR and LSF. 
 • Imaging Modified Response Criteria in Solid Tumors (m-RECIST) will be used on follow-up multiphase CT or MRI at 1, 3 and 6 months post Y90 radioembolization • Tumor dose response threshold will be determined • Imaging parameters for both Y90 SPECT and PET in both low and therapeutic dose will be optimized with the goal of recommending one of either SPECT or PET as the feasible imaging modality of choice at the conclusion of the study.

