1.3 Schedule of Activities (SoA)

Study Flow Chart for Individual Patients

Estimated Timeline for Weeks 1-2 (Mapping and Treatment Week)

Monday:

7:30 AM-9:30 AM: 1st Angiographic study for mapping and MAA delivery

10:00 AM-11:00 AM: MAA SPECT/CT (Patient will go to nuclear medicine with radial/femoral arterial access sheath in place)

11:30 AM-1:00 PM: 2nd Angiographic study for low-dose Y90 delivery (After the procedure, patient's femoral sheath will be removed and hemostasis will be achieved with manual compression or closure device. If procedure performed via radial access, which is more commonly performed currently at Emory, the radial sheath will stay in and removed according to IR protocol after Y90 SPECT/CT.)

2:00 PM-3:00 PM: Y90 Bremsstrahlung SPECT/CT

3:00 PM-3:30 PM: Removal of the radial sheath at IR post procedural area and discharge.

4:30-5:30 PM: Y90 PET/CT.

Patient is free to go home after this.

Thursday:

11:00 AM-12:30 PM: 3rd angiographic study to deliver therapeutic dose of Y90.

1:00 PM-2:00 PM: Y90 Bremsstrahlung SPECT/CT (After the procedure, patient's femoral sheath will be removed and hemostasis will be achieved with manual compression or closure device. If procedure performed via radial access, which is more commonly performed currently at Emory, the radial sheath will stay in and removed according to IR protocol after Y90 SPECT/CT.)

3:00 PM-3:30 PM: Removal of the radial sheath at IR post procedural area and discharge.

4:30-5:30 PM: Y90 PET/CT.

Patient is free to go home after this.

Study Procedures	Screening Visit Week 0	Therapy planning/mapping Week 1-2	Y90 sirsphere treatment Week 1-2	1 week post procedure Week 6	1 month post procedure Week 6	3 months post-procedure Week 14	6 months post-procedure Week 26
Informed consent	X						
Entry Criteria	X						
Demographics	X						
Medical/surgical Hx	X						
Blood sampling	X				X	X	X
Collect list of medications	X						
Vital signs	X						
Physical exam	X						
Phone follow-up by [name] or Research Nurse				X			
MRI W & WO contrast	X				X	X	X
Conventional MAA angiography		X					
Low dose Y90 shunt study angiography		X					
SPECT/CT		X	X				
PET/CT		X	X				
Y90 Treatment			X				
Post Procedure Clinic follow up					X	X	X

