4. STUDY DESIGN

4.1 Overall Design

This study is a single arm phase II prospective clinical trial in which patients with HCC who are deemed suitable for Y90 radioembolization will be recruited. Patients will undergo standard of care mapping study with ^{99}Tc -MAA to plan for Y90 radioembolization therapy. The additional, non-standard of care, intervention will be to do a second mapping study using low-dose Y90 (15 mCi) before the therapeutic Y90 radioembolization.

The distribution of MAA in terms of lung shunt fraction (LSF) and tumor to normal liver activity ration (TNR) will be compared to that of low-dose Y90. The treatment planning will be performed using standard of care MAA biodistribution using partition dosimetry model.

After administration of therapeutic Y90 dose, the actual dose delivered to tumor, non-tumoral liver (NTL) and lungs will be compared to the dose predicted by MAA and low-dose Y90.

The patients will be followed-up clinically and with imaging at 1, 3 and 6 months to determine tumor response, potential treatment related toxicity and to determine TDRT.

Hypothesis: Low dose Y90 microspheres as the treatment planning radiotracer will allow more accurate prediction of therapeutic Y90 liver biodistribution, which will enable us to perform prospective personalized dosimetry for every individual patient.

The results of this study will determine the safety and efficacy of using low dose Y90 as a direct surrogate for treatment planning to ensure delivering cytotoxic Y90 dose to the targeted tumor(s), while concomitantly minimizing liver and lung toxicity with more accurate prediction of therapeutic Y90 biodistribution. **Our long-term objective is to increase the likelihood of objective tumor response, prolonged progression-free survival (PFS) and overall survival (OS) in patients with HCC treated with Y90 RE.**

The study is a single-arm in study in which each patient will undergo two sets of mapping procedure before the actual Y90 therapy. One with standard of care ^{99}Tc -MAA and one with low-dose (15 mCi) Y90 microspheres. **Therefore, the additional intervention in the study is the second mapping procedure with low-dose Y90 microspheres.** Each patient will be used as their internal control to minimize selection biases. **Additional to standard of care Y90 SPECT/CT after therapy, the patient will undergo one PET/CT after low-dose Y90 and one PET/CT after Y90 therapy.**

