10. STATISTICAL CONSIDERATIONS

10.1 Study Design/Endpoints

Primary Objective Endpoints:

A) Accuracy/Efficacy: The accuracy/efficacy of MAA as a predictor of therapeutic Y90 distribution will be compared to that of low-dose Y90.

H₀: Y90 will have the same LSF as MAA.

H_A: Y90 will have significantly less LSF than MAA.

H₀: Y90 will have the same TNR as MAA.

H_A: Y90 will have significantly higher TNR than MAA.

B) Safety: adverse events related to Y90 radioembolization and angiography will be document by physical examination, clinical laboratory test and cross-sectional imaging.

No statistical consideration applied to the safety portion of the primary end point as it is a single arm study in which every patients undergo both mapping procedures with MAA and low-dose Y90. Detailed safety analysis plan is outlined below in section 10.5.

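### The primary objective compares the safety of low-dose Y90 with MAA, but the single-arm fixed sequence allows no comparison of adverse event rates between the two tracers

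*Combined protocol and SAP*

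**What the plan says.** The synopsis (section 1.1) and section 3 give the same primary objective: "To compare the safety and accuracy/efficacy of low dose Y90 resin microspheres and MAA in predicting the actual dose delivered" to tumor, liver and lung. In section 3 the endpoint for the safety half is that "adverse events related to Y90 radioembolization and angiography will be document by physical examination, clinical laboratory test and cross-sectional imaging"; it is not split by tracer. The synopsis names LSF and TNR as the primary endpoint and lists toxicity as secondary. Section 4.1, like the study description in the synopsis, goes further: "The results of this study will determine the safety and efficacy of using low dose Y90 as a direct surrogate for treatment planning".

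On design, section 4.1 says that "each patient will undergo two sets of mapping procedure before the actual Y90 therapy" and that "Each patient will be used as their internal control to minimize selection biases". The Monday timetable in section 1.3 reads "7:30 AM-9:30 AM: 1st Angiographic study for mapping and MAA delivery", then "11:30 AM-1:00 PM: 2nd Angiographic study for low-dose Y90 delivery". Therapeutic Y90 follows on Thursday in section 1.3, and on Wednesday or Thursday in section 8.1 (item H).

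On analysis, section 10.1 states: "No statistical consideration applied to the safety portion of the primary end point as it is a single arm study". Section 10.5 plans frequency tables and proportions.

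**The concern.** Using each patient as their own control works for LSF and TNR, because each tracer is imaged separately. It does not work for toxicity that is looked for once, after all three administrations. An event weeks after therapy cannot be assigned to the mapping dose rather than the therapeutic dose. An absence of events cannot show that low-dose Y90 mapping is as safe as MAA mapping, because no patient has MAA mapping and therapy without it. If the objective keeps its wording, a report could answer it with a comparative safety statement that has no comparator behind it.

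**Working it through.** **1. The plan's own figure.** There is none for safety. The only sample size is n=30 in section 10.2, for LSF: difference 11.66 × 0.5 = 5.83 points, SD of the paired difference 10.2 × √(2 − 2 × 0.5) = 10.2. A two-sided 5% paired t-test with equal SDs needs n=27 for 80% power, and n=30 gives 85.7%. The plan does not state sidedness. The stated number is conservative on this reading and has no bearing on the safety question.

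**2. Exposure windows from the timetable (sections 1.3, 7.5 and 8.1).**

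| Window | Calculation | Length |
|---|---|---|
| MAA only | 9:30 to 11:30, or to 13:00 | 2 to 3.5 h |
| MAA and low-dose Y90, before therapy | Mon 13:00 to Wed 11:00, or to Thu 11:00 | 46 to 70 h |
| After therapy | section 7.5 | about 180 days |

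The first row takes MAA as injected at the end of its slot, because section 8.1 (item B) puts arterial access, catheterization, angiography and cone-beam CT before the injection. Counting from 7:30 would give 5.5 h, an outer bound that treats the start of the procedure as the injection. For the second row, the outer bound (Mon 11:30 to Thu 12:30) is 73 h. The order never varies, and the arterial sheath stays in place between the two Monday procedures, so an access-site event after 11:30 belongs to both.

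**3. Overlap of the two Y90 doses.** With the 64.1 h half-life in section 7.2.4, the fraction of low-dose activity left at therapy is 2^(−t/64.1): 61% at 46 h and 47% at 70 h. The second irradiation begins when roughly half or more of the first is still to be delivered.

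**4. When the named harms would be seen.** Section 11.1 lists radioembolization-induced liver disease, radiation pneumonitis and gastroduodenal ulcer. After therapy, the scheduled contacts are a 1-week telephone call and visits with laboratory tests and imaging at 1, 3 and 6 months (section 8.1, items L to O). The table in section 1.3 shows no blood sampling between mapping and therapy. Delayed toxicity is therefore observed only after MAA and both Y90 doses.

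**5. Which sections capture the MAA period.**
- Section 9.1 makes patients evaluable for toxicity from first Y90 therapy.
- Section 10.5 counts events that start once Y90 has been given, without saying whether that means the mapping or the therapeutic dose.
- Section 11.5.1 runs from treatment allocation, for events that begin or worsen after consent.

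Under the first two, the MAA-only window is empty by construction. Section 11.5.1 could fill it, but its form asks for start and end dates, and MAA and low-dose Y90 share a date. Section 10.5 does list time of onset.

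**6. What 30 patients can describe.** With 0 events in 30, the one-sided 95% upper limit is 1 − 0.05^(1/30) = 9.5%, and the two-sided limit is 1 − 0.025^(1/30) = 11.6%. At a 1% risk (the ceiling in section 2.3 for serious vascular injury or bleeding), the chance of seeing at least one event is 1 − 0.99^30 = 26%. At 2% (the section 11.1 figure for misplaced microspheres), it is 1 − 0.98^30 = 45%. These figures describe the whole sequence.

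**The case against.** The best defense is that the plan never carries out the comparison. Section 10.1 gives the single-arm design as its reason for applying no statistics to safety. In section 3 only the accuracy endpoint speaks of comparing, section 10.5 is descriptive, section 10.5.4 rules out between-cohort toxicity comparisons, and the synopsis lists toxicity as secondary. All of that stands. A reader might infer that the plan is set to conclude that low-dose Y90 is safe compared with MAA, but no planned analysis produces that result. What remains is an objective and a section 4.1 claim that the analysis cannot meet.

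A reader might also infer that no adverse event difference of any kind could be observed. That is too strong. An acute event before the low-dose injection, such as bleeding or a contrast reaction, can be assigned to the first procedure. Section 11.4.2 requires a causality assessment, and the section 11.5.1 form separates investigational, non-investigational and indistinguishable causes. These are judgements on single events, over unequal windows in a fixed order, and they do not amount to a comparison of rates.

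Nor is the gap before therapy unobserved. Section 8.2 asks for a full physical examination on the day of Y90 therapy, and section 8.1 images chest and abdomen after the low dose alone. The first does not reach delayed toxicity, and the second shows where the activity went, not clinical harm.

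Finally, the safety objective might mean the safety of planning with low-dose Y90. That reading fails too: sections 7.1.2 and 8.1 (item G) set the treatment activity from MAA SPECT and keep the Y90 calculations for post-hoc analysis, so no patient is treated on a Y90-based plan.

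**Conclusion.** The concern holds in limited form. The documents state a comparative safety objective that the design cannot meet: adverse event rates cannot be compared between tracers, and there is no contrast for delayed radiation toxicity. The MAA-only window is about 2 to 3.5 h, the low-dose window before therapy about 46 to 70 h, and the remaining 180 days or so follow all three administrations. What can be estimated is the safety of the full sequence, with an upper limit of 9.5% (one-sided 95%) if no events occur. This rests on the printed timetable being followed and on MAA being injected near the end of its slot; a longer MAA-only window, even 5.5 h, would not change the conclusion.

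A reader might infer that the trial's main analysis fails. The documents do not support that: LSF and TNR are measured per tracer, and their hypotheses, sample size and primary analysis are untouched.

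**What to change.** - **Objective.** In the synopsis and sections 3, 4.1 and 10.1, restate the safety objective as describing the safety of adding low-dose Y90 mapping to standard MAA mapping and Y90 therapy. Drop the claim that the study will determine the safety of low-dose Y90 planning relative to MAA. State once whether safety is a primary or a secondary endpoint.
- **Collection.** Reconcile the start points in sections 9.1, 10.5 and 11.5.1 so that adverse events for analysis are collected from the first mapping procedure. Record clock time of onset on procedure days.
- **Analysis.** In section 10.5, tabulate events by onset window: MAA to low-dose Y90, low-dose Y90 to therapy, and after therapy. Attribute the last window to the combined sequence, and state that no MAA-versus-Y90 safety inference will be made.

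The cost is a weaker safety claim and slightly more adverse event recording. No extra patients, visits or tests are needed. The onset-window table depends on the collection change: without it, the first column would be empty under section 10.5, and calendar dates could not separate the first two. Keeping a comparative objective would instead need a concurrent MAA-only group. As an illustration, detecting 1% against an assumed 5% takes 285 patients per arm (80% power, two-sided 5%), far beyond this study.

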4. STUDY DESIGN

4.1 Overall Design

This study is a single arm phase II prospective clinical trial in which patients with HCC who are deemed suitable for Y90 radioembolization will be recruited. Patients will undergo standard of care mapping study with ^{99}Tc -MAA to plan for Y90 radioembolization therapy. The additional, non-standard of care, intervention will be to do a second mapping study using low-dose Y90 (15 mCi) before the therapeutic Y90 radioembolization.

The distribution of MAA in terms of lung shunt fraction (LSF) and tumor to normal liver activity ration (TNR) will be compared to that of low-dose Y90. The treatment planning will be performed using standard of care MAA biodistribution using partition dosimetry model.

After administration of therapeutic Y90 dose, the actual dose delivered to tumor, non-tumoral liver (NTL) and lungs will be compared to the dose predicted by MAA and low-dose Y90.

The patients will be followed-up clinically and with imaging at 1, 3 and 6 months to determine tumor response, potential treatment related toxicity and to determine TDRT.

Hypothesis: Low dose Y90 microspheres as the treatment planning radiotracer will allow more accurate prediction of therapeutic Y90 liver biodistribution, which will enable us to perform prospective personalized dosimetry for every individual patient.

The results of this study will determine the safety and efficacy of using low dose Y90 as a direct surrogate for treatment planning to ensure delivering cytotoxic Y90 dose to the targeted tumor(s), while concomitantly minimizing liver and lung toxicity with more accurate prediction of therapeutic Y90 biodistribution. **Our long-term objective is to increase the likelihood of objective tumor response, prolonged progression-free survival (PFS) and overall survival (OS) in patients with HCC treated with Y90 RE.**

The study is a single-arm in study in which each patient will undergo two sets of mapping procedure before the actual Y90 therapy. One with standard of care ^{99}Tc -MAA and one with low-dose (15 mCi) Y90 microspheres. **Therefore, the additional intervention in the study is the second mapping procedure with low-dose Y90 microspheres.** Each patient will be used as their internal control to minimize selection biases. **Additional to standard of care Y90 SPECT/CT after therapy, the patient will undergo one PET/CT after low-dose Y90 and one PET/CT after Y90 therapy.**

The study is a single center (Emory) single site study. For the convenience of patients and in order to obtain additional PET/CT's on the same day as the mapping and Y90 therapy on a state-of-the-art PET scanner, all mapping and therapy procedures for each patient will be performed at either Emory University Hospital Midtown or Emory University Hospital.

The remainder of the study will be standard of care will imaging and clinical follow-up at 1,3, 6 months in IR clinics. Additionally, patient will be follow-up by phone at 1-week post therapy. The data analysis in terms of the actual dose delivered to the tumor, NTL and lung and the accuracy of MAA vs. low-dose Y90 to predict the respective doses will not require additional patient visits.

4.2 Scientific Rationale for Study Design

As discussed in detail in 2.1, there is growing evidence that factoring individual patient characteristics into Y90 treatment planning are likely to significantly impact both TR and treatment tolerability. To this end, the partition model, while more resource intensive, has made great strides towards treatment individualization. However, the use of MAA in predicting post Y90 RE absorbed dose and biodistribution is flawed and inaccurate, leading to suboptimal dose delivery, unnecessary hepatotoxicity and poor outcomes. **Therefore, we propose low-dose Y90 microspheres for therapy planning, as an alternative to MAA, to be a bioidentical therapeutic Y90 surrogate marker to better predict and thus achieve optimal therapeutic dosing.** Our long-term goal is to improve TR, PFS, and OS while reducing potential associated toxicities in patients treated with Y90 RE.

4.3 Justification for Dose

Based on our phantom study to minimize scatter on SPECT/CT and to ensure adequate activity to be imaged using PET, 15 mCi of low-dose Y90 is found to be adequate. Additionally, in a hypothetical patient with a LSF of 100% (usually ~10% in HCC patients), 15 mCi of Y90 activity will result in 27.8 Gy of radiation to the lungs which is within the accepted limits of 30 Gy per treatment session. Such patient will not be a candidate a for therapeutic Y90 dose so cumulative dose to the lungs will remain below 30 Gy.

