5. STUDY POPULATION

5.1 Inclusion Criteria

Study candidates must meet all of the following inclusion criteria to be eligible for participation in this study:

- a. Adults \geq 18 years
- b. Life expectancy of 6 months or more as determined by the investigator
- c. HCC confirmed by Liver Reporting & Data System (LIRADS) on MRI or CT
- d. Must have measurable disease, defined as at least one lesion that can be accurately measured in at least one dimension (longest diameter to be recorded for non-nodal lesions and short axis for nodal lesions) as \geq 20 mm (\geq 2 cm) with CT scan, MRI, or calipers by clinical exam. See Section 12 (Measurement of Effect) for the evaluation of measurable disease.
- e. \leq 3 lesions
- f. Longest dimension of the largest lesion \leq 7cm
- g. Single lobe disease
- h. No significant extrahepatic metastatic disease
- i. Barcelona Clinic Liver Cancer Stage A, B or C
- j. ECOG $<$ 2 (Appendix A)
- k. Lesion(s) $<$ 50% of liver volume
- l. Bilirubin \leq 2 mg/dL
- m. Albumin \geq 3 g/dL
- n. PT/INR $<$ 2
- o. AST/ALT \leq 3 institutional upper limit of normal (ULN)
- p. Platelet count $>$ 50,000/mcL
- q. Lung shunt fraction of $<$ 20% by planar MAA if dose modification results in inadequate dose delivered to the tumor(s)
- r. Patients with a prior or concurrent malignancy whose natural history or treatment does not have the potential to interfere with the safety or efficacy assessment of the investigational regimen are eligible for this trial.
- s. Completion of all previous therapy (including surgery, radiotherapy, chemotherapy, immunotherapy, or investigational therapy) for the treatment of cancer \geq 12 week before the start of study therapy.
- t. Willingness and ability of the subject to comply with scheduled visits, drug administration plan, protocol-specified laboratory tests, other study procedures, and study restrictions.
- u. Evidence of a personally signed informed consent indicating that the subject is aware of the neoplastic nature of the disease and has been informed of the procedures to be followed, the experimental nature of the therapy, alternatives, potential risks and discomforts, potential benefits, and other pertinent aspects of study participation.
- v. The effects of *Y90 microspheres* on the developing human fetus are unknown. For this reason female of child-bearing potential (FCBP) must have a negative serum or urine pregnancy test prior to starting therapy.

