7.1.2 Dosing and Administration

Treatment will be administered on an *outpatient* basis. Reported adverse events and potential risks are described in Section 7. Appropriate dose modifications are described in Section 8. No investigational or commercial agents or therapies other than those described below may be administered with the intent to treat the patient's malignancy.

No dose escalation or dose expansion is planned in this procedure.

The treatment Y90 dose will be calculated using the partition model as detailed below:

The required therapeutic Y90 dose will be calculated using MAA SPECT, Y90 SPECT and Y90 PET. **Although all 3 sets of calculations will be made prospectively, the activity calculation based on MAA SPECT (the standard of care) will be used for actual treatment planning.** The activities calculated using Y90 SPECT and PET will be used for post-hoc analysis. Partition model to achieve cytotoxic Target Tumor Dose of >100 Gy will be utilized using the following formulas[7]:

- 1) **Desired Tumor Activity (GBq) = (100 Gy X Tumor Mass (Kg)) / 50**
- 2) **Targeted Normal Liver Activity (GBq) = Desired Tumor Activity (GBq) / TNR**
- 3) **Targeted Liver Lobe Activity (GBq) = (Targeted Normal Liver Activity + Desired Tumor Activity) (GBq)**
- 4) **Targeted Liver Lobe Dose (Gy) = Targeted Liver Dose Activity (GBq) X 50 / Liver mass (Kg)**

The liver and tumor mass will be determined using the volumes calculated by MIM software and assuming density of 1.03 g/cm³ [39]. It will be ensured that targeted liver dose remains below 50 Gy which has been shown to be safe with no sequela of radiation induced liver disease while ensuring the target tumor dose >100 Gy[7, 26].

5) Y90 Activity for administration (GBq) = Targeted Liver Lobe Activity (GBq) X (1+LSF)

Lung dose after therapeutic Y90 RE will be calculated using the following formula:

6) Lung Dose (Gy) = Y90 Activity to be Administered (GBq) X LSF X 50 / Mass of Lungs (Kg)

Lung Dose <30Gy will be ensured by reducing administered activity if needed (lung mass assumed at 1 Kg)[8].

The MAA, low-dose and therapeutic dose Y90 microspheres will be administered intra-arterially using the following technique:

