7.1.3 Dose Modifications

In patients with LSF of $\geq 20\%$, the therapeutic dose to the tumor will be modified to ensure <30 Gy to the lungs while maintaining >100 Gy to the tumor if possible.

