v. **Y90 Activity for administration (GBq) = Targeted Liver Lobe Activity (GBq) X (1+LSF)**

Lung dose after therapeutic Y90 RE will be calculated using the following formula:

vi. **Lung Dose (Gy) = Y90 Activity to be Administered (GBq) X LSF X 50 / Mass of Lungs (Kg)**

Lung Dose <30Gy will be ensured by reducing administered activity if needed (lung mass assumed at 1 Kg)[8].

H. 3rd Angiography and Administration of Y90 Therapy Dose (Wednesday/Thursday)

The actual prescribed Y90 activity as calculated above using MAA SPECT (**the current standard of care**) will be administered on Wednesday or Thursday of the same week after the shunt study. The desired activity will be drawn from the remainder of activity in the 5-day flex resin microsphere vial. It will be administered by [name] using the same catheter techniques described above. **After the procedure, patient's femoral sheath will be removed and hemostasis will be achieved with manual compression or closure device. If procedure performed via radial access, which is more commonly performed currently at Emory, the radial sheath will stay in and removed according to IR protocol after Y90 SPECT/CT.** The patient will be then transported to nuclear medicine department of Y90 SPECT/CT.

I. Therapeutic-dose Y90 Planar and SPECT/CT (Wednesday/Thursday)

Using the same technique described above (section E), planar and SPECT/CT will be performed using medium energy filter. The patient will then be discharged from IR after removal of the radial sheath according to our standard protocol.

J. Therapeutic-dose Y90 PET/CT of chest and abdomen (Wednesday/Thursday)

The patient will then undergo time of flight Y90 PET/CT with one or two bed positions depending on the patient's size. This will also occur on the same day and at the same location as the remainder of mapping day either at EUH or EUHM.

Below is the conservative estimated timeline of Mapping/shunt studies performed on Wednesday or Thursday:

11:00 AM-12:30 PM: 3rd angiographic study to deliver therapeutic dose of Y90.

1:00 PM-2:00 PM: Y90 Bremsstrahlung SPECT/CT (After the procedure, patient's femoral sheath will be removed and hemostasis will be achieved with manual compression or closure device. If procedure performed via radial access, which is more commonly performed currently at Emory, the radial sheath will stay in and removed according to IR protocol after Y90 SPECT/CT.)

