10.2 Sample Size/Accrual Rate

Based on previously published data by our group, we assume mean (SD) LSF of 11.66% (10.2) for HCC using MAA[43]. Assuming LSF in low-dose Y90 is 50% lower than what is predicted by MAA and within subject correlation of 0.5 in a paired t-test, **n=30** achieves 80% power with $\alpha=0.05$. This assumption is based on several previously published studies including the work presented by our own that demonstrate that MAA overestimates true Y90 LSF by as high as 100% [25, 35-37]. Assuming mean (SD) TNR of 5.4 (2.1) using MAA is 30% lower than low-dose Y90, the power achieved with n=30 is greater than 99% [8, 25].

Emory University Hospital is one of the busiest liver transplant and cancer centers in United States. Annually, 150 HCC patients who may be transplant/surgical or palliative therapy candidates are referred to interventional radiology (IR) at Emory for liver directed therapies. Assuming a conservative accrual rate of 30%, we predict an enrollment of **n=30** patients in 6-8

months. In the event that a patient drops out either after being consented or after having a part of the study completed, a new patient will be recruited.

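### Section 4.3 relies on a very high Y90 shunter going untreated, but no dosing rule uses the low-dose Y90 LSF and formula 6 omits the 15 mCi mapping activity

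*Combined protocol and SAP*

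**What the plan says.** Section 4.3 takes a hypothetical patient with an LSF of 100%, gives 27.8 Gy as the lung dose from 15 mCi, and calls this "within the accepted limits of 30 Gy per treatment session". It then makes a cumulative statement about that patient: "Such patient will not be a candidate a for therapeutic Y90 dose so cumulative dose to the lungs will remain below 30 Gy". Section 7.1.1 relies on this argument to say that the mapping dose carries no pneumonitis risk when LSF is high.

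The operating sections say the following.

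- **Planning (7.1.2, 8.1 G).** Activity is calculated from MAA SPECT, Y90 SPECT and Y90 PET before therapy, but MAA SPECT is used to plan. For the rest: "The activities calculated using Y90 SPECT and PET will be used for post-hoc analysis".
- **Administration (8.1 H).** What is given is "The actual prescribed Y90 activity as calculated above using MAA SPECT".
- **Lung dose (7.1.2, formula 6).** "Lung Dose (Gy) = Y90 Activity to be Administered (GBq) X LSF X 50 / Mass of Lungs (Kg", with a lung mass of 1 kg and activity reduced if needed to stay under 30 Gy.
- **Dose modification (7.1.3).** At an LSF of 20% or more the dose is changed "to ensure <30 Gy to the lungs while maintaining >100 Gy to the tumor if possible". No tracer is named.
- **Eligibility (5.1 q).** LSF must be under "20% by planar MAA if dose modification results in inadequate dose delivered to the tumor(s".
- **Discretion (7.6, 7.7, 11.1).** The investigator decides on management after a significant finding, inability to receive Y90 is a reason for withdrawal, and lung dose is to be held to 30 Gy. None of these sets a low-dose Y90 trigger.

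**The concern.** The safety argument for the study's one added Y90 administration depends on recognizing a very high shunter and not treating that patient. The scan that would show such a patient is done on Monday and its calculations on Tuesday or Wednesday, before therapy. Yet no rule tells anyone to act on it. Separately, the only lung-dose calculation made before therapy counts the therapeutic activity alone, although every patient has already received 0.555 GBq through the same hepatic artery branches. Followed as written, formula 6 understates the lung dose the patient will have received by the end of therapy. What is at stake is patient safety and the truth of a stated safeguard, not the trial's primary inference.

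**Working it through.** **1. The plan's own figure.** 15 mCi x 0.037 = 0.555 GBq. Formula 6 at LSF 100% and 1 kg gives 0.555 x 1.0 x 50 / 1 = 27.75 Gy, which agrees with the stated 27.8 Gy.

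**2. What formula 6 leaves out.** The mapping dose adds 27.75 Gy x LSF: 2.8 Gy at 10%, 5.6 Gy at 20%, 8.3 Gy at 30%.

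**3. Inputs for worked cases.** Tumor dose 100 Gy and density 1.03 g/cm3 (7.1.2); TNR 5.4 (10.2); at most three lesions, the largest up to 7 cm (5.1). Assumption: spherical lesions, all 7 cm.

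- One lesion: 179.6 cm3 x 1.03 = 0.185 kg.
- Formula 1: 100 x 0.185 / 50 = 0.370 GBq. Formula 2: 0.370 / 5.4 = 0.0685 GBq. Formula 3: lobe activity 0.438 GBq.
- Three lesions: lobe activity 1.315 GBq.
- Formula 5: administered activity A = lobe activity x (1 + LSF).

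**4. A typical case.** One 7 cm lesion, LSF 10% on both tracers: A = 0.438 x 1.10 = 0.482 GBq (13.0 mCi). Formula 6 shows 2.4 Gy; mapping adds 2.8 Gy; the total is 5.2 Gy. Formula 6 shows less than half the total, but the total is far below 30 Gy.

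**5. Where formula 6 passes but the total exceeds 30 Gy, tracers agreeing (L = LSF).** The lower edge solves (0.555 + lobe x (1+L)) x L x 50 = 30. The upper edge solves lobe x (1+L) x L x 50 = 30.

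| Lesions (7 cm) | Lower edge | Upper edge |
|---|---|---|
| One | 49.6% | 77.2% |
| Three | 27.0% | 34.0% |

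For three lesions at LSF 30%: A = 1.315 x 1.30 = 1.710 GBq; formula 6 gives 25.65 Gy; mapping adds 8.33 Gy; the total is 33.98 Gy. This case also needs a targeted liver mass above 1.315 kg to satisfy formula 4 (1.71 kg if the formula 5 activity is used). Supply does not prevent it: 83 mCi x 0.037 = 3.07 GBq remains on Thursday (7.2.4).

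**6. The same case under the plan's own assumption.** Section 10.2 states "we assume mean (SD) LSF of 11.66% (10.2) for HCC using MAA" and takes low-dose Y90 LSF as 50% lower. With MAA LSF 30% and Y90 LSF 15%: (0.555 + 1.710) x 0.15 x 50 = 17.0 Gy. More generally, if formula 6 holds the MAA-based dose to 30 Gy and the true LSF is half, therapy gives at most 15 Gy and mapping at most 27.75 x 0.5 = 13.9 Gy. The total is at most 28.9 Gy at any tumor load.

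**7. Tracers disagreeing the other way.** With MAA LSF 10%, the total reaches 30 Gy at a Y90 LSF of 0.6 / (0.555 + 0.482) = 57.8% for one lesion, or 0.6 / (0.555 + 1.447) = 30.0% for three. MAA would have to under-read about 3 to 6 times.

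**The case against.** The case for leaving the text alone is substantial.

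- **Scope of 4.3.** Its cumulative statement concerns only a hypothetical 100% shunter, and 30 Gy is described there as a per-session limit. Mapping and therapy are separate sessions. A reader might infer that a total of 34 Gy breaches the protocol's limit; the documents do not support that. This stands. However, 11.1 gives the 30 Gy limit without mentioning sessions, so the protocol should say which reading applies.
- **Existing safeguards.** MAA is imaged before low-dose Y90 is given, so a patient who also shunts heavily on MAA comes under 5.1(q) and 7.1.3 first. Every window in the working lies above an LSF of 20%, where 7.1.3 already applies and which section 2.1 treats as a relative contraindication. This stands for tracers that agree, except that 7.1.3 points back to a lung-dose formula without the mapping term.
- **Direction of error.** Section 2.1 reports that MAA overpredicts LSF. At a ratio of 0.5 the excess disappears. This stands as an average expectation, not a guarantee for each patient: the same section reports a correlation of only 0.682 between MAA and measured Y90 LSF.
- **Frequency.** A reader might apply the planning mean and SD of LSF to the 27-34% window and infer a count of affected patients out of 30. That is not supported: the window belongs to three 7 cm lesions, the eligibility maximum, and the documents give no joint distribution of LSF and tumor load.
- **MAA planning is deliberate.** It preserves standard of care. This stands, and the fix leaves it in place.

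**Conclusion.** The point holds as a gap between a stated safeguard and the operating rules. No text turns a high low-dose Y90 LSF into a decision about therapy, and formula 6 omits 27.75 Gy x LSF from a dose every patient has received. At ordinary LSF the omission is a few Gy and does not bring the total near 30 Gy in the worked cases. A total above 30 Gy is rare. It needs a large tumor load with an LSF of 27-34%, or a much higher LSF with one lesion, and it mainly concerns a patient whose Y90 LSF is not below the MAA LSF.

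These sizes assume spherical 7 cm lesions, TNR 5.4, a lung mass of 1 kg and exactly 100 Gy to tumor. Because 100 Gy is a floor in 7.1.2, a higher prescription moves the windows to lower LSF.

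A reader might also infer that the efficacy result is compromised. It is not: the paired MAA versus low-dose Y90 comparison of LSF and TNR uses scans obtained before therapy. The point is worth fixing because the safety signal is already in hand before treatment and using it is cheap.

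**What to change.** Keep MAA-based planning and the existing MAA formula 6 cap. In 7.1.2, 7.1.3 and 8.1 G:

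1. Report the mapping contribution alongside the formula 6 result.
2. Add one pre-therapy safety check, stated to be cumulative over mapping plus therapy: (0.555 GBq + planned therapeutic activity) x low-dose Y90 SPECT LSF x 50 / 1 kg. SPECT is preferred because the phantom in 2.2.2 read 6.9% by SPECT and 4.9% by PET against a true 7.5%.
3. If the result is 30 Gy or more, reduce therapeutic activity below 0.6/LSF - 0.555 GBq (from 30 = (0.555 + A) x LSF x 50) or withhold therapy. If 100 Gy to the tumor then cannot be reached, the investigator decides.
4. Cross-reference the rule in 4.3. At LSF 100% it leaves under 0.6 - 0.555 = 0.045 GBq, so the 4.3 statement is then backed by a rule.
5. Record each case where therapy changed.

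The mapping term should not force a cut on the MAA LSF alone. With three lesions and MAA LSF 30%, that would lower tumor dose to about 84 Gy even if Y90 SPECT read 15% and the total were 17.0 Gy. Section 2.1 itself warns of underdosing from a falsely high MAA LSF.

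The cost is a few lines of text and one case report form field; the scans and calculations are already scheduled before therapy. The downside is that a rare patient has therapy reduced or withheld on a SPECT reading made with an energy window adapted for same-day Tc-99m. With three lesions and both tracers at 30%, activity falls from 1.710 to 0.6/0.30 - 0.555 = 1.445 GBq and tumor dose to 100 x 1.445/1.710 = 84.5 Gy.
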